#### **4.2 Randomization, blinding and unblinding procedures**

No randomization, blinding or unblinding procedures are planned for this study.

### **5 Analysis Sets and Cohorts**

Analysis Sets are described as follows:

- Enrolled analysis set (ENR) defined as all subjects who provided informed consent.
- Safety Analysis Set (SAF), defined as all subjects who received at least one dose of ALM-488

QMS Document Name: Statistical Analysis Plan	Page 9 of 29
QMS No (include version ref): STF-015-GL.02	Document date: 09JUL2019
CONFIDENTIAL	

- Dose-Limiting Toxicity (DLT) Evaluable Set, defined as subjects who receive ALM-488 and either 1) complete the safety follow-up through the DLT evaluation period (i.e., Day 15 ± 8) or 2) experiences a DLT at any time during the DLT evaluation period.
- Activity Analysis or Full Analysis Set (FAS), defined as all subjects in SAF who also received at least one evaluable image.
- Pharmacokinetics (PK) Analysis Set defined as all subjects who completed a PK blood sampling period without any major protocol violations which would render the data unreliable. The PK will be the primary analysis set for the pharmacokinetic analyses. PK of analyses will be fully described in the PK SAP.

SAF will be used for all safety analyses. FAS will be used for all efficacy analyses. The PK Analysis Set will be used for all PK analyses; ENR set will be the primary analysis set for disposition and listings. PP set will constitute the primary analysis set for early efficacy. DLT Evaluable Analysis Set will be used to assess the tolerability of ALM-488 in the dose escalation phase.

The Dose Escalation/De-Escalation cohort (Cohort A) consists of all dose escalation/de-escalation cohorts: Cohort A1, A2, A3, A4, A5, A6. In case of DLT rate = 0 or special FDA requests additional cohorts may be added to the tables.

The Dose Time Determination cohort (Cohort B) consists of: Cohort B1 - dose administration 3-5 hours in advance of surgery, and Cohort B2 - dose administration 1-3 hours in advance of surgery.

If not otherwise stated in the respective section, the statistical analyses will be performed for the following analysis sets:

Analyses	ENR	FAS	DLT	SAF	PK
Disposition	✓				
Demographics and baseline characteristics				✓	
Medical history				✓	
Exposure and compliance				✓	
Previous and concomitant therapies				✓	
Early Efficacy		✓			
Pharmacokinetic					✓
Safety				✓	
Dose-Limiting Toxicity			✓		
Listings		✓		✓	

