## 3 Modification History

### 3.1 Changes to the Planned Analyses

The statistical analyses as specified in this SAP are mostly consistent with the statistical analyses as specified in the study protocol version Amendment 1, 24 August 2020.

We propose to include two additional specific analysis sets ENR, and DLT. They will allow to better describe the different steps of the study. They are not defined in the protocol. The additional analysis sets are defined below in section 5.

This SAP has been updated based on changes associated with protocol amendment 1.0.

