The aim is to determine the lowest possible dose that achieves adequate imaging performance (nerve identification) with an acceptable toxicity profile. The Safety Review Committee (SRC) will determine the Optimal Dose based on 1) the safety data and 2) adequacy of fluorescence observed in each of the dose groups. Following determination of the Optimal Dose, Dose Timing Cohorts will

QMS Document Name: Statistical Analysis Plan	Page 8 of 29
QMS No (include version ref): STF-015-GL.02	Document date: 09JUL2019
CONFIDENTIAL	

commence at this Optimal Dose. The Dose Timing Cohorts will compare fluorescence characteristics at different ALM-488 administration times before surgery (3-5 hours, 1-3 hours).

Please refer to Section 5 of the protocol for full details on the study design.

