#### **4.1 Sample Size Estimation**

The primary objective of this study is to evaluate the safety of ALM-488 administered by intravenous (IV) infusion to subjects undergoing head and neck surgery.

At each dose level, a cohort of 3 subjects will be enrolled for safety and tolerability evaluation. If there are no subjects with a DLT at a given dose level, new subjects will be enrolled at the next dose escalation level. If there are  $\geq 1$  subjects having any DLT, the enrollment to that specific dose and dose escalation will stop. New subjects will be enrolled at the next dose de-escalation level. There will be a minimum of 3 cohorts. Given that there will be 3-6 subjects for each dose level, 9-36 subjects will be needed for the dose escalation/de-escalation cohorts.

It is anticipated that the proposed dose range (100-1000mg) is expected to yield optimal imaging performance, with an initial starting dose of 100mg that has been selected based on supportive nonclinical testing. If the 100 mg dose is found to provide adequate fluorescence imaging of nerves, a dose de-escalation schedule will be followed to ensure that the lowest effective dose is determined. If imaging at starting first de-escalated dose (75 mg) becomes less adequate compared to 100mg as determined by the SRC, then imaging at dose escalation schedule will resume - beginning at 200mg. The Optimal Dose will be determined by the SRC as the lowest possible dose and toxicity profile that achieves adequate imaging performance of nerves using WLR combined with FL.

The Dose Timing Cohort will use the Optimal Dose as defined by the SRC following completion of the Dose Escalation/De-Escalation cohorts. Subjects in the Dose Timing phase will be administered ALM-488 at two planned operative times before surgery to assess the impact of timing of administration on fluorescence image quality. This phase will consist of 2 cohorts, 6 subjects/cohort: (1) dose administration 3-5 hours in advance of surgery, (2) dose administration 1-3 hours in advance of surgery. A total of 12 subjects will be needed for the Dose Timing phase.

In summary, 9-36 subjects may be enrolled into the dose escalation/dose de-escalation cohorts and 12 subjects may be enrolled into the dose timing cohort. A total of 21-48 subjects may be enrolled into this study.

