### 9.2 *Disposition and withdrawals*

The number and relative frequency will be presented for

- Subjects completing the study
- Subjects who prematurely discontinued the study
- Reasons for study discontinuation (Adverse Event, death, lost to follow-up, physician decision, pregnancy, progressive disease, site or study terminated by sponsor, technical problems, withdrawal by subject, adverse device effect or other)
- Subjects completing surgery
- Subjects completing treatment

Completing the study is defined as having completed the infusion, surgery, and end of study telephone call.

A list of subjects' trial end date, time to trial discontinuation and reason for trial discontinuation will be created.

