### **10.4 Exposure and Compliance**

The number and percentage of subjects will be presented by individual Cohorts (i.e., Cohorts: A, A1, A2, A3, A4, A5, A6, B, B1, B2) on the SAF analysis set.

The infusion duration will be calculated in minutes as:

When there are no interruptions in infusions:

Infusion duration (minutes) = (time of infusion end – time of infusion start) + 1

When infusion interruptions will be reported the time of the interruption need to be subtracted from time of infusion.

Descriptive statistics for the treatment duration will be presented.

QMS Document Name: Statistical Analysis Plan	Page 17 of 29
QMS No (include version ref): STF-015-GL.02	Document date: 09JUL2019
CONFIDENTIAL	

The infusion completed per protocol, details if deviated as well as infusion reactions IR will be described.

Study ALM-488 dose and timing of administration and the summary of exposure will be listed by individual Cohorts (i.e., Cohorts: A, A1, A2, A3, A4, A5, A6, B, B1, B2) for the SAF Analysis Set

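### The DLT Evaluable Set has no minimum-exposure condition, so a DLT-free subject who finishes follow-up is fully evaluable however little of the infusion was given

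*SAP*

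**What the plan says.** SAP section 5 gives the DLT Evaluable Set as "defined as subjects who receive ALM-488 and either 1) complete the safety follow-up through the DLT evaluation period" (Day 15 ± 8), or who have a DLT at any time in that period. Neither route mentions an amount of drug. On the use of the set, section 5 says: "DLT Evaluable Analysis Set will be used to assess the tolerability of ALM-488 in the dose escalation phase".

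Section 3.1 introduces this set and the enrolled set as SAP additions and says of them: "They are not defined in the protocol".

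Section 5 also has a default table, introduced by "If not otherwise stated in the respective section, the statistical analyses will be performed for the following analysis sets". The table assigns dose-limiting toxicity to the DLT set. Section 12 names no set for its criterion (1), which requires no DLT in a cohort of three, so the default applies. Section 12 also describes the dot plot, with an open circle for every subject without a DLT. Section 20.3 lists that plot as Figure 14.3.1, on the DLT set.

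Elsewhere the SAP treats infusion completion as a status of its own:
- Section 9.2: "Completing the study is defined as having completed the infusion, surgery, and end of study telephone call".
- Section 10.4: "The infusion completed per protocol, details if deviated as well as infusion reactions IR will be described". The same section corrects infusion duration for interruptions.
- Section 14.1 plans a listing of adverse events that led to stopping study medication.

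None of these is linked to DLT evaluability.

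**The concern.** A subject who tolerated part of a dose is weaker evidence about the full dose than a subject who tolerated all of it. Section 5 counts the two alike. In a cohort of three, one such subject is a third of the evidence, and nothing in the dot plot would show it.

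The error has a direction. If DLT risk does not fall as dose rises, a partly dosed subject is no more likely to have a DLT than a fully dosed one, so the count can only look the same or better for the dose. A subject with a DLT is counted at any exposure, which is right. The looseness affects only the DLT-free side.

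At stake is whether a reported 0 of 3 at a dose level means what section 12 needs it to mean: three subjects given that dose, none with a DLT.

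**Working it through.** **1. The plan's own figures.** Section 4.1 gives 3 to 6 subjects per level and at least 3 cohorts; section 4 gives up to 6 cohorts; the timing phase has 2 × 6 = 12 subjects.
- Minimum: 3 × 3 = 9, and 9 + 12 = 21.
- Maximum: 6 × 6 = 36, and 36 + 12 = 48.

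These match the stated 9-36 and 21-48. The SAP gives no operating characteristics for the 0-of-3 criterion, so there is no further figure to reproduce.

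**2. What the rule does.** Suppose three subjects are infused, one infusion is stopped for good part-way, and all three complete follow-up without a DLT. Under section 5 all three are evaluable. Section 12 criterion (1) reads 0 of 3, and Figure 14.3.1 shows three open circles. Two subjects had the full dose.

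**3. Size in an affected cohort.** Let p be the DLT rate at full dose and k the partly dosed subject's risk relative to full dose. The documents give neither, so both are assumptions.

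P(0 of 3, one partly dosed) = (1 − p)² × (1 − k·p)

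| p | k = 1 (no reduction) | k = 0.5 | k = 0 (extreme) |
|---|---|---|---|
| 30% | 0.70² × 0.70 = 0.343 | 0.70² × 0.85 = 0.417 | 0.70² × 1 = 0.490 |
| 20% | 0.80² × 0.80 = 0.512 | 0.80² × 0.90 = 0.576 | 0.80² × 1 = 0.640 |

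**4. Size averaged over cohorts.** Let t be the chance that an infusion is incomplete (also not in the documents).

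P(0 of 3) = [(1 − t)(1 − p) + t(1 − k·p)]³, at p = 30%, against 0.343:
- t = 5%: k = 0.5 gives 0.7075³ = 0.354; k = 0 gives 0.715³ = 0.366.
- t = 10%: k = 0.5 gives 0.715³ = 0.366; k = 0 gives 0.73³ = 0.389.

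The average shift is about 1 to 5 percentage points.

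**5. The opposite error.** Dropping reaction-stopped subjects and counting only completers would also bias the count. If 10% would be stopped for a reaction and carry an assumed 60% DLT risk, against 30% overall, completers' risk is (0.30 − 0.10 × 0.60) / 0.90 = 0.267. P(0 of 3) is then (1 − 0.267)³ = 0.394, against 0.343. Under-dosed subjects therefore have to stay visible, with the reason.

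**The case against.** The strongest reply is that the set is not shown to steer dosing. The escalation rule in section 4.1 counts subjects with a DLT and names no analysis set. Section 4 says: "The Safety Review Committee (SRC) will determine the Optimal Dose based on 1) the safety data and 2) adequacy of fluorescence". Section 17 sends cohort-by-cohort safety outputs to a separate charter. Among the listed tables, listings and figures, only Figure 14.3.1 is assigned to the DLT set; the DLT listing is on the FAS. This stands. A reader might infer that section 5 would let an unsafe dose escalate, but the documents do not support that.

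Second, the missing rule may exist. The protocol text available holds only part of the study summary. The DLT definition, infusion-stopping rules and any replacement rule are not in it. Section 4.1 enrols three per cohort and then says "Given that there will be 3-6 subjects for each dose level", without saying how a level grows beyond three. Section 3.1 says only that the set is absent from the protocol, so one cannot infer that the protocol has no conduct rule. If stopping for a related reaction is itself a DLT, only non-toxicity stops remain. This stands as a limit, but a conduct rule elsewhere would not change section 5's definition.

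Third, the shortfall would be seen. Sections 10.4 and 14.1 report completion, deviations, infusion reactions and events leading to stopping. The 12 timing-cohort subjects add safety data at the Optimal Dose on the SAF. This is also true, but it leaves a reader of the 0-of-3 result to reassemble the evidence from other outputs.

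Fourth, size. One might contrast exact one-sided 95% upper bounds on the DLT rate of 63% for 0/3 (1 − 0.05^(1/3)) and 78% for 0/2 (1 − 0.05^(1/2)), and say that the SAP claims the tighter one. It plans no such bound, and the contrast gives a partly dosed subject no information at all. The contrast is not relied on here.

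Finally, the difference between sections 9.2 and 5 is not a contradiction. Disposition and DLT evaluability serve different purposes. It shows only that incomplete infusion is foreseen.

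**Conclusion.** The point holds within limits. Followed as written, section 5 counts a DLT-free subject with a truncated infusion and completed follow-up as fully evaluable. The result can read 0 of 3 in the tolerability assessment, in section 12 criterion (1) and in Figure 14.3.1 when fewer than three subjects had the full dose. The link to criterion (1) rests on the default table.

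The effect is confined to a cohort with an incomplete infusion that was not itself a DLT. At an assumed 30% DLT rate with one of three partly dosed, the chance of 0 of 3 is 42% at half the risk and at most 49%, against 34%. Averaged over cohorts it is small. The direction assumes that DLT risk does not fall with dose; the DLT rate, the relative risk and the frequency of incomplete infusions are all assumptions.

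This is a defect in how tolerability is counted and shown. It is not evidence that the SRC would choose a wrong dose. It is worth correcting because the SAP foresees the case and the correction is cheap.

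**What to change.** In section 5, add:
- A subject without a DLT is evaluable only if the planned infusion was completed (including after a pause), or if at least a stated fraction of the planned mg, fixed before analysis, was received.
- A subject with a DLT is evaluable at any amount.
- All infused subjects stay in the SAF.

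In section 12, name the DLT Evaluable Set in criterion (1). Report under-dosed DLT-free subjects separately with the reason, for example 0/2 fully dosed plus 1 incomplete (technical stop, or reaction below DLT level). In Figure 14.3.1, give them their own symbol, so that they remain visible although they are outside the evaluable count.

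Leave replacement to the protocol, since it is trial conduct, and cross-refer to any minimum-dose or replacement rule there.

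The cost is a few lines of SAP text and one plot symbol, using infusion data already planned in sections 10.4 and 10.5. If a fraction of mg is used, confirm that the dose summarised in 10.5 is the amount received; the section does not say. The real downside is that the evaluable count in an affected cohort may fall below three, so that criterion (1) cannot be met on three evaluable subjects there unless the protocol allows a further subject. One more would take a level from 3 to 4, within the planned 3 to 6, and would add that subject's own DLT period (Day 7 to Day 23).

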## ***8.4 Missing data***

Only observed data will be summarized for all Cohorts. Except for partial or missing dates, no imputation for missing data is planned for the summary or analyses of these study data.

The missing component(s) of incomplete dates (e.g. start and/or stop dates of AE, concomitant medication, medical history) will be assumed as the most conservative value possible. For example, if the start date has a missing day value, the first day of the month will be imputed for study day computations, etc. If day is missing for an end date, the last day of the month will be imputed. If the start date has a missing month value, the first month of the year will be imputed for study day computations, etc. If month is missing for an end date, the last month of the year will be imputed. For determination of treatment-emergent status, the start date will be imputed as the date of the first dose of study drug, unless there is clear evidence (through comparison of partial dates/times) to suggest otherwise.

Date imputation will only be used for computational purposes such as treatment-emergent status, etc. Actual data values, as they appear in the original eCRFs, will be presented in the subject data listings.

QMS Document Name: Statistical Analysis Plan	Page 14 of 29
QMS No (include version ref): STF-015-GL.02	Document date: 09JUL2019
CONFIDENTIAL	

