#### **12 Determination of Optimal Dose**

The optimal dose will be the lowest possible dose and toxicity profile that achieves adequate imaging performance: (1) DLT rate is 0 subjects for a 3-patient cohort (2) adequate fluorescence signal of nerves compared to background non-nerve tissue. A dot plot will be presented to display Cohorts A1 through A6. Cohorts A1 through A6 will be displayed on the x-axis, with a cluster of 3 to 6 dots for each cohort. The dose will be displayed on the y-axis. Dots will be open circles for subjects who do not experience a DLT. Solid red dots will be used for subjects who experience a DLT. A listing of the DLTs will also be provided.

Image intensity ratios will also be plotted with time from injection to skin incision on the x-axis, image intensity ratio on the y-axis, and a separate color for each dose level.

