#### **13 Efficacy**

The data on the signal-to-background ratio for FL and WLR will be provided by Stanford University for the different regions of interest ROIs. All efficacy analyses will be completed on the FAS Analysis Set and will be repeated in PP analysis set if the latest is different from FAS Analysis Set. The analyses using signal to background ratio SBR for cohort A will only use images produced by Zeiss camera while both Zeiss and OnLume devices will be used for timing cohort B.

QMS Document Name: Statistical Analysis Plan	Page 18 of 29
QMS No (include version ref): STF-015-GL.02	Document date: 09JUL2019
CONFIDENTIAL	

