### **13.1 Timing, Dose, Size and Intensity**

The efficacy endpoints pertaining to timing of administration, dose, and intensity (signal-to-background ratio SBR), along with the surgeon rating scale will be assessed throughout enrollment into Cohorts A1-A6 to determine the final dose for use in Cohorts B1 and B2. These efficacy endpoints will also be used to evaluate the effect of timing of administration of ALM-488 by comparison of Cohort B1 and B2. The following analyses are planned for these efficacy endpoints:

- For each Cohort, SBR will be averaged to get a single mean ratio per patient; then a paired t-test or Wilcoxon signed rank test will be used, as appropriate, to compare SBR between FL and WLR.
- SBR will be also listed by cohort type, and surgery type and device for both FL with WLR.
- Image intensity ratios will also be analyzed with repeated measures analysis of variance (RMANOVA) with timing, image, method (FL /WLR), and device (Zeiss/OnLume) as the repeated factors in the model.
- SBR for FL and WLR measurements will be plotted. Values to the right of the line will indicate that there is improved visualization with FL images and values to the left of the line will indicate that there is improved visualization with WLR images(Equal performance of FL versus WLR will be indicated by dashed line (slope = 1)].
- To further assess timing, Cohorts B1 and B2 will be compared. Image ratios will be averaged to get a single mean ratio per patient; then an unpaired t-test or Wilcoxon rank sum test will be used, as appropriate, separately for FL and WLR.

Paired t-tests will be used unless markedly non-normal data is observed including bimodal or other severe assumption violations; minor skewness is robust to the paired t-test and RMANOVA assumptions. If extreme skewness with outliers, or bimodal distributions are observed, then a Wilcoxon signed rank test will be used instead of a paired t-test and RMANOVA will be performed on the ranked data.

Similarly, unpaired t-tests will be used unless markedly non-normal data is observed including bimodal or other severe assumption violations; minor skewness is robust to the unpaired t-test assumptions. If extreme skewness with outliers, or bimodal distributions are observed, then a Wilcoxon rank sum test will be used instead.

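### The efficacy analysis set leaves out infused, operated subjects with no evaluable image, so the Cohort A rating and time-saved tables can flatter a weak dose

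*SAP*

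**What the plan says.** SAP section 5 describes the FAS as "defined as all subjects in SAF who also received at least one evaluable image" and adds that "FAS will be used for all efficacy analyses". Section 13 repeats it: "All efficacy analyses will be completed on the FAS Analysis Set". All the efficacy tables listed in section 20.1 carry the FAS label.

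Section 8.4 states that "Only observed data will be summarized for all Cohorts". Apart from partial or missing dates, "no imputation for missing data is planned for the summary or analyses of these study data".

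Section 13.1 ties these endpoints to the dose. Timing, dose, signal-to-background ratio (SBR) and surgeon rating "will be assessed throughout enrollment into Cohorts A1-A6 to determine the final dose for use in Cohorts B1 and B2". The imaging half of the Optimal Dose criterion in section 12 is an "adequate fluorescence signal of nerves compared to background non-nerve tissue", with no threshold, denominator or analysis set. Under section 4 the Safety Review Committee (SRC) decides from the safety data and the "adequacy of fluorescence observed in each of the dose groups".

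Three other provisions bear on the point:
- The surgeon rating (sections 7.3 and 13.2) is given for each image, and its lowest score means that the nerve is not seen.
- The time-saved question (sections 7.3 and 13.4) is asked once per surgery and summarized by patient.
- Section 9.1 presents the analysis sets by cohort, with reasons for exclusion.

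**The concern.** Entry to the FAS depends on something that happens after infusion and that the dose can influence: whether a usable image was obtained. If imaging fails in a subject because the signal is too weak, that failure is evidence about the dose. Yet the subject is absent from the tables that describe imaging at that dose.

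The stated aim is the lowest dose with adequate imaging, so the comparison that matters is between a lower dose and the one above it. If failures of this kind are commoner at lower doses, leaving them out narrows the visible difference between doses. Cohorts B1 and B2 then run at the dose chosen.

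The time-saved table shows the gap most plainly. The question is put for each surgery, so a subject with no evaluable image may well have an answer on file. A table restricted to the FAS discards it. That is a loss of observed data, which the rule against imputation does not require.

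**Working it through.** **1. The plan's own figures.** SAP section 4.1 has at least 3 cohorts and 3 to 6 subjects per dose; section 4 allows up to 6 dose cohorts. Minimum 3 × 3 = 9, maximum 6 × 6 = 36, timing cohorts 2 × 6 = 12, total 9 + 12 = 21 to 36 + 12 = 48. This matches the stated 21 to 48. It is a cohort count; no adequacy rate or imaging failure rate lies behind it.

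**2. Which subjects leave.**

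| Infused subject | In FAS? | Consequence |
|---|---|---|
| Evaluable image, nerve not seen | Yes | Rated 1; failure is counted |
| Operated, no evaluable image, camera or recording fault | No | Not evidence about the dose |
| Surgery not done | No | No imaging or time-saved result to lose |
| Operated, no evaluable image, non-technical reason | No | Leaves the rating and time-saved tables |

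The first row follows from section 13.1, which uses SBR to separate images rated 1 from images rated 4 to 5. Images rated 1 are therefore expected to have an SBR. Only the last row is a problem.

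**3. Effect of one exclusion.** With n subjects at a dose and one excluded, the number contributing falls from n to n − 1.
- n = 3: 3 to 2. Each remaining subject's weight rises from 1/3 = 33.3% to 1/2 = 50%.
- n = 6: 6 to 5. The weight rises from 1/6 = 16.7% to 1/5 = 20%.

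**4. What this does to a planned table.** The time-saved table reports counts and percentages by patient. Assume that the excluded subject's surgeon answered no and all the others answered yes.
- n = 3: FAS 2/2 = 100%; all operated subjects with an answer 2/3 = 66.7%.
- n = 6: FAS 5/5 = 100%; all operated subjects with an answer 5/6 = 83.3%.

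These answers are assumed, to show the arithmetic. The rating table is summarized by image, so an excluded subject simply contributes no images, and nothing in the table shows that a subject is missing.

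**5. How often a cohort would be affected.** Let f be the chance that an infused, operated subject has no evaluable image for a non-technical reason. The documents give no value, so a range is assumed. The chance of at least one such subject is 1 − (1 − f)^n; for example, 1 − 0.9³ = 1 − 0.729 = 27.1%.

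| Assumed f | n = 3 | n = 6 |
|---|---|---|
| 0 | 0% | 0% |
| 10% | 27.1% | 46.9% |
| 20% | 48.8% | 73.8% |
| 30% | 65.7% | 88.2% |
| 50% | 87.5% | 98.4% |

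**6. Direction.** The comparison between doses is tilted only if f differs by dose. Section 8.1 foresees that six dose cohorts might not give an adequate signal, so weak signal is contemplated, but no rate by dose is stated.

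**The case against.** The strongest reply is that a nerve that does not fluoresce can still be imaged and rated 1, so most weak-signal failures remain in the FAS. This stands, and it is why the point is limited to subjects with no evaluable image at all. How many there could be turns on a term the available text leaves undefined.

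Second, the SRC determines the dose, and nothing binds it to FAS tables. With 3 to 6 subjects per dose it would probably notice an infused subject without images. A reader might infer that adequacy is judged only within the FAS; sections 4 and 12 do not say so. Still, the FAS is the only set that section 5 defines for imaging results, and section 13.1 says those endpoints help determine the dose.

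Third, section 9.1 and Table 14.1.2 already give exclusions by cohort, so part of the remedy exists. That also stands. But these are disposition outputs and return nobody to an efficacy table. Listing 16.2.3, on allocation to populations, and the imaging, clinical-benefit and SBR listings (16.2.8, 16.2.17, 16.2.18) are themselves on the FAS.

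Fourth, SAP section 4 refers to protocol section 5 for the full design, and the protocol text available is the study summary. A rule on evaluability may be there. If so, the SAP should cite it and say how it acts on these tables.

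**Conclusion.** The point holds as a limited gap that is cheap to close. The efficacy set can drop dose-related imaging failures, and in the time-saved table it can drop an answer that was actually recorded. One such subject changes the denominator from 3 to 2 or from 6 to 5. The overall size is unknown, and it is nil if every infused, operated subject has an evaluable image.

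Three stronger readings are tempting, and the documents do not support them:
- *That the Optimal Dose will be set too low.* This needs failures concentrated at low doses and an SRC that relies on the FAS alone. The first is not documented and the second is not stated.
- *That the plan will report, say, 2 of 2 subjects as adequately imaged.* No listed table gives a per-subject adequacy proportion. The percentages in the working concern the time-saved question only.
- *That mean SBR is inflated by a calculable amount.* A subject with no evaluable image has no measured SBR. Giving that subject a value such as 1.0 presupposes an image that would have placed the subject in the FAS.

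The conclusion rests on two assumptions: that a non-technical absence of evaluable images can occur, and that it can depend on dose.

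**What to change.** In the SAP:
- Define an evaluable image, and record the reason when a subject has none in enough detail to separate a camera or recording fault from other causes.
- For the Cohort A surgeon-rating summary and the section 12 dose determination, add a per-subject line by dose over all infused subjects who had surgery. Count a subject with no evaluable image as 'nerve not adequately imaged' unless the recorded reason is a camera or recording fault.
- Run the time-saved table on all infused, operated subjects with an answer.
- Show the numbers infused and evaluable beside each imaging summary given to the SRC.
- Keep the FAS for SBR means.
- Reconcile the sets. Section 5 calls a PP set primary for early efficacy but neither defines it nor includes it in its table of sets, while the same section and section 13 assign efficacy to the FAS.

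The cost is SAP wording, one line per dose and a specific reason code. The sample size does not change. The downside is that adequacy at some doses may look slightly less favourable.
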